#### **Subject Recruitment and Compensation**

All adult patients (18-85 years old) Admitted to CTICU following cardiac surgery using CPB, with an admission temperature  $\leq 35.0$  °C will be considered for recruitment.

Both males and females and all demographic groups will be included.

Patients are intubated and sedated on admission to the CTICU after cardiac surgery, so informed consent will be obtained from the patient's next of kin or power of attorney by one of the patient's care providers or study personnel.

Approximately 14 patients will be included in the prospective recruitment of patients. Data will be matched with a historical cohort of 28 patients (2:1 matching).

No compensation will be offered.

#### **Consent Process**

Typically, patients remain intubated and sedated until hypothermia resolves. Patients will not be able to consent for themselves for this study. Informed consent will be obtained from next of kin / power of attorney.

#### **Risk/Benefit Assessment**

Heated humidified breathing circuits are being used clinically to avoid / treat hypothermia both in the OR and the ICU. We aim to examine if this clinical practice provides additional benefit to the forced warm air devices. Risks associated with heated humidified breathing air includes: possible inefficient warming of body temperatures, thermal injury to airways, excessive heating (hyperthermia).

There is also a potential risk of loss of confidentiality. Every effort will be made to keep your information confidential, but this cannot be guaranteed. Those risks can be minimized by frequent monitoring and documentation of both the device temperature as well as the patient temperature every 15-30 minutes to avoid over heating, and make sure active rewarming is stopped when temperature of patient exceeds 36 C.

If patient's power of attorney declined to participate in the study, only forced air warming will be used for active rewarming of patient.

Possible benefit if using warm humidified air is more effective in rewarming patients when combined with forced warm air devices than when using forced warm air devices alone, hypothermia will resolve quicker, potentially minimizing complications associated with hypothermia such as coagulopathy, shivering, metabolic derangements, etc.

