# Heated Humidified Breathing Circuit Rewarming in Hypothermic Patients after Cardiopulmonary Bypass

## Purpose of the Study

Our primary objective is to assess whether use of Heated Humidified breathing circuits (HHBC) decreases time to normothermia ( $\geq 36.5$  °C).

Our secondary objectives are to assess whether use of HHBC shorten time to extubation, improve coagulopathy, decrease bleeding, and metabolic derangements seen with hypothermia.

We propose the hypothesis that: Rewarming hypothermic patients ( $\leq 35$  °C) admitted to the CTICU following cardiac surgery with CPB, using HHBC in addition to conventional forced air warming blankets will shorten time to normothermia.

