The current standard of rewarming patients in the ICU is to use forced air heating blankets. Forced-air blankets reduce the core temperature afterdrop by 60%. However, heat-balance data indicate that this reduction resulted primarily because forced-air heating prevented the typical decrease in body heat content after discontinuation of CPB, rather than by reducing redistribution. They do not lead to clinical relevant changes in deep thigh temperature, or toe perfusion. The extra heat especially favors core temperature. This is underlined by the decrease in postoperative leg blood flow, suggesting that the majority of the warmed blood leaving the heart flows to core organs and not to the periphery.

A recent Cochrane review showed that active warming, particularly forced air warming, appears to offer a clinically important reduction in mean time taken to achieve normothermia (normal body temperature between 36°C and 37.5°C) in patients with postoperative hypothermia. However, high-quality evidence on other important clinical outcomes is lacking; therefore it is unclear whether active warming offers other benefits or harms. High-quality evidence on other warming methods is also lacking; therefore it is unclear whether other rewarming methods are effective in reversing postoperative hypothermia.

Regarding HHBC, Hyungseok et al recently showed that a heated humidifier is more effective in preventing intraoperative core temperature decrease in elderly patients than a heat moisture exchanger alone. Sooyong et al showed that a decrease in core temperature from anesthetic induction to 120 minutes after induction was lower in the HHBC group in patients undergoing hip arthroscopy. Park et al showed that HHBC influences heat redistribution in early period of thyroid surgery and can lessen the magnitude of the decrease in core body temperature. Frank et al showed that the delivery of warmed, humidified O2 via nasal canula accelerates core rewarming rate by approximately two-fold in mildly hypothermic postoperative patients. A recent fellow QI project used HHBC during rewarming of patients in the operating room following DHCA procedures found that it significantly attenuated the temperature afterdrop upon separation from CPB when compared to standard airway circuits.

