## **Design & Procedures**

Hypothermia ( $\leq 35$  °C) after cardiac surgery using CPB is not uncommon. To avoid complications associated with hypothermia, and due to absence of shivering when patient is sedated, and harmful effects of shivering when patient is awake, clinicians resort to active warming devices. Forced air warming devices are the most commonly utilized, but occasionally heated humidified breathing circuits are used as well. We plan to use both warming devices on study patients, and compare them with a historical cohort that has used forced air warming device only.

On admission to CTICU, if temperature  $\leq 35$  °C, we will attempt to recruit the patient. Patients are intubated and sedated on admission to the CTICU after cardiac surgery, so informed consent will be obtained from the patient's next of kin or power of attorney. After consent is obtained, the clinical provider will ask the patient's nurse to place a lower body forced air warming device and set to 38 °C, and ask the respiratory therapist to set up and connect a heated humidified breathing circuit.

Admission temperature and other vital signs will be recorded per CTICU standards. Other patient management decisions (ie medication changes, laboratory assessments...etc) per direction of ICU providers. Core temperature and location (esophageal, nasopharyngeal, bladder, rectal, blood) will be recorded every 15-30 minutes until normothermia reached (36.5 °C), then record per CTICU standard. Record active warming methods in nursing flow sheets (i.e. Forced air warming blanket and heated humidified breathing circuit). Record other vital signs, medications, extubation time, hourly chest tube output, and patient data per unit policy. Alert Respiratory therapy once normothermia (36.5 °C) has been achieved for discontinuation of HHBC.

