#### Exclusion Criteria:

Patients admitted to ICU on ECMO support.

For the retrospective part of the study:

We will be matching the 14 prospective patients who received both ANAPOD and forced warm air with 28 retrospective ones who presented with hypothermia that were treated with forced warm air alone without ANAPOD. Criteria should include:

- Hypothermic Patients (Temp < 35C) undergoing cardiac surgery under CPB who received forced warm air alone.
- Temp at time of ANAPOD application would be our reference point.
- Type of surgery
- Patient's BMI
- Deep hypothermic arrest

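### The risk section stops active rewarming above 36 °C, the procedures run HHBC to the 36.5 °C endpoint, and nothing says which rule governs

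*Combined protocol and SAP*

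**What the plan says.** Purpose of the Study sets the aim: "Our primary objective is to assess whether use of Heated Humidified breathing circuits (HHBC) decreases time to normothermia", with normothermia defined there as 36.5 °C or above.

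Design & Procedures uses the same figure to end the intervention: "Alert Respiratory therapy once normothermia (36.5 °C) has been achieved for discontinuation of HHBC". It also shows what the protocol means by active warming: "Record active warming methods in nursing flow sheets (i.e. Forced air warming blanket and heated humidified breathing circuit". For forced air, the instruction to the nurse is to "place a lower body forced air warming device and set to 38 °C". That is a device setting, and the section gives no patient temperature at which forced air ends.

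The Risk/Benefit Assessment offers monitoring every 15 to 30 minutes as the safeguard against overheating, and adds that staff should "make sure active rewarming is stopped when temperature of patient exceeds 36 C".

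The 36 °C figure appears in one other place. Background & Significance describes a cited review that took normothermia as "normal body temperature between 36°C and 37.5°C". That reports outside evidence and is not a rule for this study.

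**The concern.** Two current sections give different temperatures for ending the same treatment, and the gap lies directly before the primary endpoint. Every prospective patient who reaches 36.5 °C first passes through 36 to 36.5 °C. There one section keeps HHBC on and the other turns it off, together with forced air.

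If the risk section were followed, the study's warming would be withdrawn before the event it is meant to hasten. If some staff followed one section and some the other, the intervention would differ among only 14 treated patients. Either would make it harder to say what the comparison of times to 36.5 °C has tested.

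**Working it through.** **1. The two rules side by side**

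| Patient temperature | Design & Procedures | Risk/Benefit Assessment |
|---|---|---|
| 36 °C or below | HHBC on | Active rewarming allowed |
| Above 36 °C, below 36.5 °C | HHBC on | Active rewarming stopped |
| 36.5 °C reached | HHBC discontinued | Active rewarming already stopped |

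The rules conflict in the middle row only. Because Design & Procedures names both forced air and HHBC as active warming, the stop in the risk section covers both devices. For forced air it is the only written stop by patient temperature.

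**2. Is there a rule of precedence?** No section reconciles the two figures. The 36 °C may be a slip for 36.5 °C, or may echo the lower limit of the range in the background. The text does not say.

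**3. Size of the gap in degrees.** The gap is 36.5 − 36.0 = 0.5 °C. As a share of the rise to the endpoint it is 0.5 / (36.5 − start):

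- Start at the 35.0 °C eligibility limit: 0.5 / 1.5 = 33%.
- Start at 34.0 °C (my assumption, to show the range): 0.5 / 2.5 = 20%.

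These are shares of degrees, not of time or of treatment benefit.

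**4. Why "up to" 0.5 °C.** The stop can be triggered only by a reading, and readings come every 15 to 30 minutes. The cohort in Background & Significance rose from 34.7 to 38.3 °C over 8 hours, an average of 3.6 / 8 = 0.45 °C per hour. At that rate the patient gains 0.45 × 0.25 = 0.11 °C to 0.45 × 0.5 = 0.23 °C between readings. Warming could therefore continue somewhat past 36 °C, and the unwarmed stretch would often be shorter than 0.5 °C. The average is only a guide, since the same section calls the curve sigmoid.

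**5. The plan's power figure.** Inputs from Data Analysis & Statistical Considerations: 14 and 28 patients, difference 1.25 h, SD 1.3 h, alpha 0.05. For a two-sided two-sample t-test with 40 degrees of freedom, the noncentrality is 1.25 / (1.3 × √(1/14 + 1/28)) = 1.25 / 0.4255 = 2.94. Power is 81.8%, which agrees with the stated 82%. A one-sided test would give 89.3%, so the plan's figure is two-sided. The conflict does not touch this calculation if HHBC runs to 36.5 °C.

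**6. Can an effect on the result be calculated?** No. That would need rewarming rates above 36 °C with and without HHBC, and the temperature at which forced air ended in the historical cohort. The documents give neither. The controls are described only as patients "who presented with hypothermia that were treated with forced warm air alone without ANAPOD".

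**The case against.** The strongest reply is that the working instruction is clear. Design & Procedures names the staff, the device, the trigger and the action. Its 36.5 °C matches the endpoint definition and the temperature up to which frequent readings continue. The 36 °C figure occurs once as a study rule, in a narrative account of how risks are reduced, and nothing shows that bedside staff work from that account. A one-number slip is the likelier reading.

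Most of this stands, and it limits how much weight the point can bear. It does not remove the point: the risk section states an action at a stated temperature, it is the protocol's own safeguard against overheating, and for forced air there is no other written stop.

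It can also be said that a fixed forced-air stop cannot be imposed on a retrospective cohort. That is true. Correcting the number makes the prospective treatment consistent but does not make the two groups comparable on this feature.

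Two stronger readings are tempting, and the documents support neither.

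- **A reader might infer that the trial loses power, or is biased towards no effect.** That requires the risk section to be the rule followed, and some assumption about how benefit builds up by degree, which the sigmoid curve gives no reason to take as proportional. It also depends on whether the controls kept forced air above 36 °C, which is unknown.
- **A reader might infer that warming to 36.5 °C overheats patients.** That temperature is the protocol's own threshold for normothermia and lies within the range quoted in its background.

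**Conclusion.** The inconsistency is certain on the text: 36 °C in one section, 36.5 °C in another, for a treatment that ends at or just before the primary endpoint, with nothing to say which governs. Design & Procedures probably states the intended rule, and on that rule neither the treatment nor the power is affected.

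If the risk section were followed, warming would end up to 0.5 °C before the endpoint. One third of the rise is the figure for a start at exactly 35.0 °C and is not a ceiling. The matching list states "Temp at time of ANAPOD application would be our reference point", and a patient may have warmed between admission and application of the device.

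The effect on the treatment comparison cannot be determined in size or direction. This is a fault in how the intervention is defined. It should be corrected, and it is neither a demonstrated safety hazard nor a demonstrated loss of power.

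**What to change.** In the Risk/Benefit Assessment, replace the 36 °C stop with a statement that active rewarming, by HHBC and by forced air, ends once 36.5 °C is reached. This agrees with Purpose of the Study and Design & Procedures, and gives forced air an explicit stop. The cost is a wording amendment to one sentence, with no change to sample size or analysis.

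If a 36 °C stop is clinically intended, change Design & Procedures to match and then choose one of two courses:

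- Move the endpoint to 36 °C and re-justify the 1.25 h difference, the 1.3 h SD, the expected range of 45 minutes to 6 hours, and the power.
- Keep the 36.5 °C endpoint and restate the detectable difference and power for warming that ends before it.

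Only this alternative reopens the sample-size section.

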### **Data Analysis & Statistical Considerations**

Descriptive statistics will be used to evaluate patient demographics and clinical characteristics. Descriptive statistics will be summarized as mean  $\pm$  (SD) or median (interquartile range) for continuous variables and group frequencies (%) for dichotomous or categorical variables.

As all patients are expected to achieve normothermia within the study period, the primary outcome of time to normothermia will be analyzed as a numeric outcome variable. Following validation of distributional assumptions we will compare the time to normothermia between the two groups via t-test or Wilcoxon rank sum test as appropriate. It is expected that the patients will reach normothermia between 45 minutes and 6 hours after admission to the ICU.

By using a 2:1 matching ratio and a moderate level of variability (SD=1.3 hours) a study of 14 prospectively enrolled patients and 28 retrospectively matched patients would attain 82% power to detect a 1.25 hour difference between time to normothermia in the two groups at alpha level 0.05.

Secondary numeric outcomes such as time to extubation, time to normal PH, and coagulopathy lab values will be analyzed by t-test or Wilcoxon rank sum test as appropriate. Differences in categorical outcomes between treatment groups such as shivering will be analyzed via chi-square or fisher exact tests. As the patients will be matched on key confounders no further adjustment is expected to be necessary, so the moderate sample size should not limit the primary analysis. Potential subgroup analysis may be conducted in an exploratory analysis to determine if the treatment effect of ANAPOD warming is different by procedure type or patient/surgical characteristics.

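### Controls are matched 2:1 to the treated patients, but the primary test ignores the matching; if the matching works, the test is conservative and gives up some power

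*Combined protocol and SAP*

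**What the plan says.** The text on the retrospective part, placed under Exclusion Criteria, sets up the comparison: "We will be matching the 14 prospective patients who received both ANAPOD and forced warm air with 28 retrospective ones". The criteria listed there include temperature at the reference point, type of surgery, BMI and deep hypothermic arrest. Subject Recruitment and Compensation repeats the ratio: "Data will be matched with a historical cohort of 28 patients (2:1 matching").

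Data Analysis & Statistical Considerations gives the primary analysis: "we will compare the time to normothermia between the two groups via t-test or Wilcoxon rank sum test as appropriate". For secondary outcomes, "coagulopathy lab values will be analyzed by t-test or Wilcoxon rank sum test as appropriate", and "Differences in categorical outcomes between treatment groups such as shivering will be analyzed via chi-square or fisher exact tests". The same section says that, because the patients are matched on the main confounders, it expects no further adjustment to be needed. No paired, set-stratified, conditional or mixed-model analysis appears anywhere.

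The power statement takes an SD of 1.3 hours and group sizes of 14 and 28, and claims that this design "would attain 82% power to detect a 1.25 hour difference between time to normothermia in the two groups at alpha level 0.05".

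**The concern.** Matching on variables that predict the outcome makes patients in the same set resemble each other. The treated-minus-control contrast is then made within sets, and differences between sets cancel out of it. A two-sample t-test still counts those differences as error, so its standard error is larger than the real uncertainty of the estimate.

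The plan treats its matching variables as confounders, which implies that they relate to time to normothermia and that the within-set correlation is positive. Matching can justify leaving out further covariates. It does not justify leaving the matching out of the error term.

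With only 14 treated patients, the consequence is an interval that is too wide and a greater chance than necessary of reporting no difference when a real one exists.

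**Working it through.** **Inputs from the plan.** 14 treated, 28 controls, SD 1.3 h, difference 1.25 h, alpha 0.05, stated power 82% (all in Data Analysis & Statistical Considerations).

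**Assumed.** An exchangeable within-set correlation rho. The documents give none, so a range is shown.

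**1. Reproducing the stated power.** For independent groups:

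- SE = 1.3 × sqrt(1/14 + 1/28) = 0.4255 h
- df = 14 + 28 - 2 = 40
- noncentrality = 1.25 / 0.4255 = 2.94

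The two-sided t-test power is 81.8%, which matches the stated 82%. A one-sided test would give 89.3%, which does not match. The stated figure is therefore a two-sample calculation in which the matching enters only through the 1:2 ratio. This also settles which t-test is meant, since the text does not label it.

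**2. Standard error under matching.** In each set, take the treated time minus the mean of its two controls. The variance of that difference is

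SD² × [1 + (1 + rho)/2 - 2 rho] = 1.5 × SD² × (1 - rho).

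Averaging over 14 sets gives SE = 1.3 × sqrt(1.5 × (1 - rho)/14) = 0.4255 × sqrt(1 - rho). The two-sample test goes on using about 0.4255, so it overstates the SE by 1/sqrt(1 - rho).

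**3. Consequences.** These come from simulation with the plan's inputs, 60,000 trials per setting. The set-based model has treatment and 14 set effects, so its error df is 42 - 14 - 1 = 27. Its type I error was about 5% throughout.

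| rho (assumed) | SE overstated by | Type I error, two-sample t | Power, two-sample t | Power, set-based model |
|---|---|---|---|---|
| 0 | 0% | 4.9% | 81.6% | 80.7% |
| 0.1 | 5% | 3.9% | 83.1% | 84.9% |
| 0.2 | 12% | 3.0% | 84.5% | 88.6% |
| 0.3 | 20% | 2.2% | 86.0% | 92.3% |
| 0.4 | 29% | 1.4% | 87.5% | 95.5% |

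At rho = 0.3 the mean 95% interval is 1.70 h wide with the two-sample test and 1.45 h with the set-based model. The chance of missing a true 1.25 h difference is 100 - 86.0 = 14.0%, against 100 - 92.3 = 7.7%.

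**4. The rank branch.** The plan allows a rank sum test if the distributional check fails, so a matched counterpart is needed.

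- *Van Elteren test stratified by set.* With 14 sets of three, each set contributes only the treated patient's rank, coded -1, 0 or 1. The variance of the sum is 14 × 2/3 = 9.33, so the asymptotic cut-off is 1.96 × sqrt(9.33) = 5.99 and the test rejects at 6 or more. Its exact size is 7.0%. The exact version rejects at 7 or more, with size 3.1% and power of only 60% to 82% for rho from 0 to 0.4. The planned rank sum test has about 80% to 85% over that range.
- *Wilcoxon signed-rank test on the 14 set differences.* At rho = 0 its power is about 76%, against about 80% for the rank sum test. The two break even near rho = 0.1.

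**The case against.** **The matching may not form sets.** Neither section on matching mentions sets, tolerances or an algorithm. Two controls for each treated patient is the natural reading, but matching at group level is not excluded. This stands, and the fix must cover both cases. It does not rescue the planned analysis: with group-level matching the usual remedy is to adjust for the matching variables, which the plan does not expect to do.

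**The size rests on an assumed rho.** This also stands. The plan's own premise supports a positive sign but not a value, and with no tolerances given the matching may be coarse. At rho = 0.1 the gain is under 2 points (84.9 - 83.1 = 1.8). At rho = 0 the planned t-test is correct and the set-based model is slightly worse.

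**The stated power is not undermined.** This is correct. At every positive rho shown, the planned t-test has more than 82% power.

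**Stronger readings that a reader might draw.** One is that the planned p-values risk false positives. With positive correlation they err the other way. Another is that all the benefit of matching is lost. It is not: power of the planned test rises from 81.6% at rho = 0 to 87.5% at rho = 0.4, because the estimate itself becomes more precise. What is missing is full credit for that in the standard error and interval. A third is that the chi-square and Fisher tests should be replaced too. No gain has been shown there, and conditional methods use only sets with discordant outcomes, of which 14 sets may supply few.

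**Conclusion.** The mismatch is real: the design is matched, while the planned analysis of numeric outcomes uses independent-samples tests without adjustment. The result is a conservative test and an interval that is too wide, not excess false positives and not an error in the stated sample size. If rho lies between 0.2 and 0.4, a set-based model gains about 4 to 8 points of power for the primary outcome (88.6 - 84.5 = 4.1; 95.5 - 87.5 = 8.0). At rho = 0.1 it gains about 2 points, and at zero it loses about 1.

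The conclusion assumes individual matched sets, exchangeable correlation, roughly normal times and a positive rho. Only the sign of rho has support in the documents, and that is indirect. The point is worth correcting before analysis, because switching to a matched method after seeing an unpaired result would be a data-driven choice.

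**What to change.** In Data Analysis & Statistical Considerations:

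1. State whether each treated patient has two identified controls or the groups are matched as a whole.
2. If there are sets, make the primary analysis a linear model for time to normothermia with treatment and matched set (14 sets, 27 error df). Report the within-set difference in hours with its 95% confidence interval.
3. If there are no sets, fit a linear model with treatment and the matching variables: starting temperature, surgery type, BMI and deep hypothermic arrest.
4. If a rank method is needed and sets exist, use the Wilcoxon signed-rank test on the 14 set differences (treated minus the mean of its two controls), not the van Elteren test.
5. Use the same set-based model for secondary numeric outcomes. No change to the categorical tests is proposed.
6. State that the 82% power assumes zero within-set correlation.

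**Cost.** Revised wording and, where sets exist, a set identifier in the dataset; no further patients. If the matching proves uninformative, the set-based model costs about 1 point of power (80.7% against 81.6%). The signed-rank branch costs about 4 points at rho = 0 (76% against 80%).

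### Time to a fixed 36.5 °C is compared with historical controls without adjusting for starting temperature, and the matching meant to replace adjustment has no temperature tolerance and no reference point that exists in controls.

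*Combined protocol and SAP*

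**What the plan says.** The outcome is time to normothermia at a fixed threshold of 36.5 °C (Purpose of the Study; Design & Procedures). The study will treat patients with both warming methods and "compare them with a historical cohort that has used forced air warming device only", so the comparison is not randomised.

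Under Data Analysis & Statistical Considerations, "we will compare the time to normothermia between the two groups via t-test or Wilcoxon rank sum test as appropriate". The same section adds that "As the patients will be matched on key confounders no further adjustment is expected to be necessary". It gives 82% power for a 1.25 h difference with SD 1.3 h, 14 against 28 patients and alpha 0.05.

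The matching criteria are in the retrospective list printed under Exclusion Criteria: temperature, type of surgery, BMI and deep hypothermic arrest. On temperature the list has two lines. Controls are "Hypothermic Patients (Temp < 35C) undergoing cardiac surgery under CPB who received forced warm air alone", and "Temp at time of ANAPOD application would be our reference point". The section gives no tolerance, matching algorithm or balance check. The prospective Inclusion Criteria use an admission temperature at or below 35.0 °C.

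On timing, Design & Procedures starts the device after consent ("After consent is obtained, the clinical provider will ask" the nurse and respiratory therapist to set up the warming). The statistical section says "It is expected that the patients will reach normothermia between 45 minutes and 6 hours after admission to the ICU".

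**The concern.** Because the endpoint is a fixed temperature, a patient who starts warmer has less far to go. At 0.45 °C/h, 35.0 °C to 36.5 °C takes 1.5/0.45 = 3.3 h, and 34.0 °C to 36.5 °C takes 2.5/0.45 = 5.6 h. Starting temperature is therefore directly prognostic.

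The plan relies on matching alone to balance it, and the matching is not specified tightly enough to carry that weight. With no tolerance, controls that fit on surgery type, BMI and circulatory arrest may fit poorly on temperature. With the reference point tied to device application, nothing says when a control's temperature is read. The two groups could be matched at different points of a rising curve. If treated patients start systematically warmer, a head start can look like a device effect. If they start colder, a real effect is easier to miss.

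**Working it through.** **1. The plan's power.** SE = 1.3 × √(1/14 + 1/28) = 0.4255 h, and 1.25/0.4255 = 2.94. The noncentral t with 40 df at two-sided 0.05 gives 81.8%, so the stated 82% reproduces.

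**2. Hours per degree.** Background & Significance reports a mean rise from 34.7 to 38.3 °C over 8 h: (38.3 − 34.7)/8 = 0.45 °C/h. As a cross-check, the midpoint of the expected 45 min to 6 h is (0.75 + 6)/2 = 3.375 h. That gives 1.5/3.375 = 0.44 °C/h from 35.0 °C, or 1.8/3.375 = 0.53 °C/h from 34.7 °C. The same background paragraph calls the curve sigmoid, so a constant rate is an approximation.

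**3. Shift from a systematic gap.** 0.1/0.45 = 0.22 h and 0.2/0.45 = 0.44 h, which are 18% and 36% of the 1.25 h target.

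**4. Planned t-test if matching induces no within-set correlation.**
- No true effect: 0.22/0.4255 = 0.52 gives 8.0% rejection, and 0.44/0.4255 = 1.04 gives 17.5%.
- Gap against the device: (1.25 − 0.22)/0.4255 = 2.42 gives 65% power, and (1.25 − 0.44)/0.4255 = 1.89 gives 46%.
- Over assumed rates of 1.0 to 0.3 °C/h, rejection is 5.6-11.9% for 0.1 °C and 7.4-33.4% for 0.2 °C.

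**5. Planned t-test if controls are matched closely.** This was simulated with 0.45 °C/h, total SD 1.3 h, two controls per treated patient within an assumed ±0.1 °C, and an assumed temperature SD of 0.2 / 0.3 / 0.4 °C.

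| Systematic gap | Rejection with no true effect | Power if the gap runs against the device |
|---|---|---|
| none | about 4 / 2.5 / 1% | about 83 / 85 / 89% |
| 0.1 °C | about 7 / 5 / 3% | about 66-71% |
| 0.2 °C | about 16 / 14 / 11% | about 45% |

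With no gap the test is conservative: matching makes the group means positively correlated, and the unpaired standard error ignores this.

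**6. Adjusted model** (treatment plus starting temperature, 39 df). Rejection is about 5% at gaps of 0, 0.1 and 0.2 °C. With close matching and no gap, power is about 86 / 91 / 98%, against 83 / 85 / 89% unadjusted. With an adverse gap and no matching correlation, it is 83 / 90 / 97% at 0.1 °C and 77 / 88 / 96% at 0.2 °C, against 65% and 46% unadjusted.

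**7. Cost if temperature predicts nothing.** Losing one degree of freedom alone gives 81.7%. Allowing also for chance covariate imbalance in unmatched groups gives about 80.7%, roughly 1 point below 81.8%.

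**8. The two entry limits.** Ignoring matching, and assuming normal admission temperatures (mean 35.0-36.0, SD 0.5-0.9 °C, recorded to 0.1), controls would be 0.06-0.09 °C colder. With matching, only treated patients at exactly 35.0 °C (9-38% under those assumptions) lack an equal control. Pairing them at 34.9 °C leaves a mean gap of 0.01-0.04 °C and 5.0-5.4% rejection.

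**The case against.** The strongest reply is that temperature is already matched and that no imbalance has been shown. Both statements are true. The 8% and 17% figures need a gap that is systematic, runs in one direction and survives matching without any induced correlation. Under close matching, a 0.1 °C gap barely moves the false-positive rate. The power loss from an adverse gap remains, and so does the conservatism when matching succeeds.

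A reader might infer four stronger things that the documents do not support.

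- *Any leftover temperature difference biases the test.* It does not. Chance differences are already in the standard error: with wholly unmatched groups and no systematic gap, simulated rejection is about 5.0%.
- *The limits of ≤35.0 and <35 °C build in a colder control group.* Purpose of the Study and Design & Procedures define hypothermia as ≤35 °C, so the control wording is probably loose. Under matching its effect is negligible.
- *The plan contradicts itself on time zero.* The mention of ICU admission is in a sentence about expected times, and device application is named as the reference in a matching list. Neither formally defines time zero. The gap is a missing definition.
- *The power figure is wrong.* It is correct for the unpaired test with balanced groups.

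The sponsor could also say that not expecting adjustment does not forbid it, and that descriptive statistics on clinical characteristics are planned. But an adjustment chosen after seeing an imbalance is less credible than one fixed beforehand.

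**Conclusion.** The point holds as a recommended change. The plan rests the validity of a non-randomised comparison on matching whose temperature criterion lacks both a tolerance and a reference time in controls, and it then expects to omit the covariate that most directly determines the outcome. Whether the result is a false signal, a masked effect or a conservative test depends on how matching turns out, which the documents do not settle. In each case examined, adjustment gives about the nominal error rate and more power than the unpaired test.

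The sizes rest on a constant 0.45 °C/h, SD 1.3 h, and assumed gaps, temperature SDs and matching width. The simulations also assume a linear effect of temperature measured without error. At an assumed reliability of 0.8 (temperature SD 0.3 °C), 0.04 and 0.09 h of the 0.22 and 0.44 h shifts would remain, with 5.1% and 5.7% rejection. Adjustment does not remove other differences between the historical and current cohorts.

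**What to change.** 1. Define time zero, and the temperature at time zero, by one event that exists in both groups' records. Reconcile the Inclusion Criteria, the retrospective matching list and Data Analysis & Statistical Considerations on the temperature limit and the starting point.
2. State a matching tolerance for temperature, and report starting temperature by group.
3. Replace the sentence that expects no adjustment. Make the primary analysis a linear model of time to normothermia (log scale if skewed) on treatment and time-zero temperature. Keep the unpaired t-test or Wilcoxon test as a sensitivity analysis.
4. Label 82% as the power of the unpaired test.

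No patients are added. The statistical cost is about 1 point of power if temperature predicts nothing, so the sample size is no reason to leave out one covariate. The practical cost is a check, before the plan is fixed, that control charts hold a temperature at the chosen time zero: the 15-30 minute recording in Design & Procedures is described for study patients only.
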